4.1. Sample Size

A sample size of $n_1 = 30$ patients per treatment group in Part 1 with an additional $n_2 = 85$ patients recruited to each of the optimal recAP dose and placebo treatment groups in Part 2 (for a total sample size of $n = 290$ patients) is planned. Recruitment will continue during the interim analysis, so the total number of patients will exceed 290. Custom programmed simulations were performed using SAS[®] Version 9.2 (SAS Institute, Inc, Cary, North Carolina) to determine power and type I error rate of the chosen sample size and design under a number of different dose response scenarios. Each scenario assumed a standard deviation of 49 mL/min for the primary endpoint (area under the time-corrected endogenous creatinine clearance curve from Day 1 to Day 7 [AUC₁₋₇]) with an assumed response of 60 mL/min for the placebo group, and between 60 mL/min (no treatment effect) and 79 mL/min (strong treatment effect) for the recAP dose groups.

Fifty-thousand simulations were performed to show that the 1-sided type I error rate is 2.4% (and hence is well controlled at the 1-sided 2.5% significance level). The power was defined as the probability of rejecting the null hypothesis (of no difference between treatment groups) when 1 or more recAP dose groups have an effective treatment effect, defined as a response of 69.5 mL/min. This was investigated across 7 scenarios with 10 000 simulations performed for each. In the most realistic scenarios (with strong treatment effects, i.e., responses of 79 mL/min for the medium and high recAP dose groups and a varying response of between 60 mL/min and 79 mL/min for the low-dose group) the chosen design achieved power of between 79% and 86%. This dropped to 66% to 67% for other scenarios where only the high recAP dose group had a strong treatment effect.

4.2. Randomization, Stratification, and Blinding

Patients will be randomly assigned to receive either placebo or 1 of 3 doses of recAP using a 1:1:1:1 allocation ratio. The randomization schedule is stratified by site. Once it has been

decided which is the most optimal dose of recAP on the primary endpoint to be administered in Part 2, the codes for the treatment groups corresponding to the 2 dropped doses will be discontinued, and treatment allocation will continue using the codes for the remaining treatments on the same schedule.

An interactive voice response system (IVRS) will be used to administer the randomization schedule. An independent PPD statistician generated a permuted block randomization schedule using SAS[®] Version 9.2 (SAS Institute, Inc, Cary, North Carolina) for IVRS, which will link sequential patient randomization numbers to treatment codes. Each patient will be assigned a randomization number which will be separate from the patient identification number. Once a randomization number has been allocated to a patient, it will not be assigned to another patient.

All persons involved in the study (including but not limited to the patient, site staff, AM-Pharma B.V. team members, and PPD blinded team members [i.e. those not involved with the interim analysis and DMC]) will be blinded to treatment assignment. The randomization schedule will be held by an independent PPD team at a different regional location and will not be revealed until all patients have completed the study and the database has been finalized for the end of the study, except for the unblinded interim analysis and DMC (see [Section 11](#)). To maintain the blind, the DMC and interim analyses will be conducted and delivered by an unblinded PPD Biostatistics team located at a different site to the blinded PPD biostatistics personnel involved in the study.

4.3. Analysis Set

In accordance with International Conference on Harmonisation (ICH) recommendations in guidelines E3 and E9, the following analysis sets will be used for the analyses.

4.3.1. All Enrolled

The all Enrolled Set includes all patients that have been assigned a patient number in either Part 1 or Part 2 of the study regardless of whether they were randomized or received study drug. Patients will be analyzed according to the treatment they were randomly assigned to, with a “Not randomly assigned” treatment group (screening failures) included if required.

4.3.2. Intent-to-Treat Combined

The Intent-to-Treat (ITT) Combined Set includes all patients who were randomly assigned to a study drug in either Part 1 or Part 2 of the study, excluding patients recruiting whilst the interim analysis is performed to treatment arms not selected for Part 2. This is the primary analysis set for the efficacy analyses, and patients will be analyzed according to the treatment to which they were randomly assigned.

4.3.2.1. ITT Part 1

The ITT Part 1 Set includes all patients who were randomly assigned to a study drug prior to the conclusion of Part 1 of the study excluding patients enrolled during the interim analysis on placebo and the selected optimal recAP dose group (these patients will be included in Part 2 of the study). This analysis set will be used to compare patients enrolled during the different parts of the study. Patients will be analyzed according to the treatment they were randomly assigned to.

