**Study Design:**

This is a randomized, double-blind, placebo-controlled, 4-arm, parallel-group, proof-of-concept, and dose-finding adaptive Phase 2a/2b study.

A minimum of 290 patients with SA-AKI will be enrolled in the study. The study involves 2 parts (Part 1, Part 2) with an interim analysis between the parts, with continued recruitment during this interim analysis. Of the 290 planned patients, at least 120 patients will enroll in Part 1 and 170 patients will enroll in Part 2 with an estimated 50 patients during the interim analysis. Patients enrolled during Part 1 and during the interim analysis will be randomly assigned to receive, by 1-hour intravenous (IV)

infusion, either placebo (Part 1;  $n_1 = 30$ ) or one of 3 different doses of recAP (Part 1;  $n_1 = 30$  in each dosing arm; i.e., 0.4 mg/kg [250 U/kg], or 0.8 mg/kg [500 U/kg], or 1.6 mg/kg [1000 U/kg]) using a 1:1:1:1 allocation ratio. Patients will receive study drug by 1-hour IV infusion once daily for 3 days (Days 1, 2, and 3). The interim analysis on the primary endpoint will be performed on all data collected after the 120th patient of Part 1 has completed the Day 7 visit of the study to select the dose to be administered in Part 2. The dose chosen will be the optimal dose of recAP on the primary endpoint in Part 1, provided there are no safety issues with that dose as judged by the DMC. In Part 2, patients will be randomly assigned to receive, by 1-hour IV infusion, either placebo ( $n_2 = 85$ ) or the dose of recAP ( $n_2 = 85$ ) selected during the interim analysis. Patients recruited during the interim analysis period to the dose selected in Part 2 will form part of the Part 2 populations, but those recruited to the doses that are not selected will be included in the Part 1 population.

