## **5 Study Drugs**

### **5.1 Method of Assigning Patients to Treatment Groups**

Patients will be randomly assigned to receive either placebo or one of 3 doses of recAP using a 1:1:1:1 allocation ratio in Part 1. The randomization schedule will be stratified by site. Once it has been decided which is the optimal dose of recAP on the primary endpoint to be administered in Part 2, the codes for the treatment groups corresponding to the 2 dropped doses will be discontinued, and treatment allocation will continue using the codes for the remaining treatments on the same schedule.

An interactive voice response system (IVRS) will be used to administer the randomization schedule. An independent PPD statistician will generate a permuted block randomization schedule using SAS® software Version 9.2 or later (SAS Institute, Inc, Cary, North Carolina) for IVRS, which will link sequential patient randomization numbers to treatment codes. Each patient will be assigned a randomization number which will be separate from the patient identification number. Once a randomization number has been allocated to a patient, it may not be assigned to another patient.

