## 7.4 Sample Size Calculations

A sample size of  $n_1 = 30$  patients per treatment group in Part 1 with an additional  $n_2 = 85$  patients recruited to the optimal recAP dose and placebo treatment groups in Part 2 (for a total sample size of  $n = 290$  patients) is planned. Recruitment will continue during the interim analysis so the total number of patients may exceed 290 patients. Patients recruited during this period to the dose selected in Part 2 will form part of the Part 2 populations, but those recruited to the doses that are not selected will be included in the Part 1 population. Custom programmed simulations were performed using SAS software Version 9.2 to determine power and type I error rate of the chosen sample size and design under a number of different dose response scenarios. Each scenario assumed a standard deviation of 49 mL/min for the primary endpoint ( $AUC_{1-7}$ ) with an assumed response of 60 mL/min for the placebo group, and between 60 mL/min (no treatment effect) and 79 mL/min (strong treatment effect) for the recAP dose groups.

Fifty-thousand simulations were performed to show that the 1-sided type I error rate is 2.4% (and hence is well controlled at the 1-sided 2.5% significance level). The power was defined as the probability of rejecting the null hypothesis (of no difference between treatment groups) when 1 or more recAP dose groups have an effective treatment effect, defined as a response of 69.5 mL/min. This was investigated across 7 scenarios with 10 000 simulations performed for each. In the most realistic scenarios (with strong treatment effects, i.e., responses of

79 mL/min for the medium and high recAP dose groups and a varying response of between 60 mL/min and 79 mL/min for the low-dose group) the chosen design achieved power of between 79% and 86%. This dropped to 66% to 67% for other scenarios where only the high recAP dose group had a strong treatment effect.

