## 7.5 Analysis Sets

The following analysis sets will be used in the statistical analyses:

- **All enrolled set:** all patients enrolled in the study. Patients will be analyzed according to the treatment they were randomly assigned to, with a “Not randomly assigned” treatment group included if required.
- **ITT combined set:** all patients who were randomly assigned to a study drug. This is the primary analysis set for the efficacy analyses, and patients will be analyzed according to the treatment to which they were randomly assigned.
- **ITT Part 1 set:** all patients who were randomly assigned to a study drug prior to the conclusion of Part 1 of the study. This analysis set will be used to compare patients enrolled during the different parts of the study. Patients will be analyzed according to the treatment they were randomly assigned to.
- **ITT Part 1 interim set:** all patients who were randomly assigned to a study drug prior to the conclusion of Part 1 of the study and were included in the interim analysis. Patients will be analyzed according to the treatment they were randomly assigned to.
- **ITT Part 2 set:** all patients who were randomly assigned to a study drug after the conclusion of Part 1 of the study. This analysis set will be used to compare patients enrolled during the different parts of the study. Patients will be analyzed according to the treatment they were randomly assigned to.
- **Per-protocol (PP) Day 1-7 combined set:** all patients who were randomly assigned to a study drug, had no significant protocol deviations (e.g., wrong drug volume received, administration of prohibited concomitant medication, patient did not meet all inclusion criteria or met 1 or more exclusion criteria) and had complete data for the primary endpoint. The primary endpoint will be analyzed for the PP Day 1-7

combined set, with patients analyzed according to the treatment they received. See Section 10.2.2 and the Significant Protocol Deviation Rules document for further information on the handling of protocol deviations for this study.

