3.4. Dose Adjustment/Modifications

Infusion of the study drug may be temporarily interrupted or permanently discontinued for a variety of reasons, including an adverse event or equipment malfunction. Therefore, it is possible that the total study drug dose and volume planned for a patient may differ from the total dose and volume administered and any such patients will be identified on the study drug infusion listing (see [Section 7.2](#)).

4. General Statistical Considerations

Combined analysis of primary endpoint

As described in [Section 8.1.1](#), the primary efficacy endpoint for this study is analyzed at both the interim analysis (based on all patients recruited in Part 1 up to that point) and at the end of the study (using all patients recruited after conclusion of Part 1, i.e. during Part 2). Patients recruited whilst the interim analysis is performed will be handled as follows:

- Those recruited to the optimal dose or placebo will form part of the Part 2 populations.
- Those recruited to the other doses will not be included in any efficacy analysis (except one sensitivity analysis on the primary endpoint), but their safety data will be analyzed.

The results from each analysis are then combined using an inverse normal method. This combined analysis of patients from Parts 1 and 2 rests on the assumption that patients recruited in each part of the study will belong to the same overall patient population. To check this assumption, data related to the baseline characteristics and demographics (for the selected optimal dose and placebo groups) will be repeated for Part 1 and Part 2. If any notable differences are observed, then the combined analysis will need to be interpreted with caution and further exploratory analysis will need to be conducted to investigate the possible causes.

The assumption of a consistent treatment effect across Parts 1 and 2 will be investigated by repeating the primary and key secondary efficacy analyses (for the optimal recAP dose and placebo treatment groups) for Part 1 and Part 2. Again, any notable differences will lead to the associated combined analysis being interpreted with caution and further exploratory analyses conducted to investigate the possible causes.

Combined analysis of secondary and ‘other’ endpoints

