8.2.2. Other Secondary Efficacy Endpoints

Unless stated otherwise all analysis on the other secondary endpoints will compare the optimal recAP with placebo and be based on the ITT Combined Set, i.e. include all patients randomized to those treatment groups during Part 1 and Part 2 of the study. All summary statistics, counts and percentages, and data listings will be based on the ITT Combined Set, displaying results for all four treatment groups and including all patients randomized during Part 1 or Part 2 of the study.

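### The SAP removes patients randomised to unselected doses during the interim analysis from ITT Combined and from the four-arm efficacy summaries, contrary to the protocol and without recording the change

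*SAP*

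**What the plan says.** **Protocol.**
- Section 7.5 defines the ITT combined set as "all patients who were randomly assigned to a study drug. This is the primary analysis set for the efficacy analyses". It makes no exception.
- Section 7.4, like the synopsis and Section 3.1, says of patients recruited while the interim analysis runs that "those recruited to the doses that are not selected will be included in the Part 1 population".
- Section 7.7.1 ends by asking for the descriptive AUC1-7 summary in all four groups for everyone randomised before Part 2.

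**SAP, the exclusion.**
- Section 4, second bullet on interim-period recruits: "Those recruited to the other doses will not be included in any efficacy analysis". It allows one unnamed sensitivity analysis on the primary endpoint and keeps their safety data.
- Section 4, first sentence on secondary and other endpoints: repeats the exclusion for the four-group efficacy summaries.
- Section 4.3.2 writes it into the set definition: "excluding patients recruiting whilst the interim analysis is performed to treatment arms not selected for Part 2".

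**SAP, text that points the other way.**
- Section 8.2.2 describes the ITT Combined summaries as "including all patients randomized during Part 1 or Part 2 of the study".
- Table 12-1 says the secondary summaries show all four treatments for all patients, on the same footing as safety.
- Section 4.3.3.1 (PP Day 1-7 Combined) has no matching exclusion, and Section 8.1.1 compares each dose with placebo in that set.

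SAP Section 12, which lists changes from the protocol's analysis, does not mention the exclusion.

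**The concern.** A set labelled ITT, and named as the primary efficacy set, leaves out randomised patients. They are out because of the arm they were assigned to and a dose decision taken after they were randomised. Placebo patients randomised alongside them are kept, in Part 2. The protocol does not provide for this, and the SAP does not declare it as a change.

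Two practical problems follow. A programmer cannot satisfy Sections 4 and 4.3.2 together with the literal text of 8.2.2 and Table 12-1. The combined per-protocol set, meant as a supplement to ITT, can also contain patients who are not in ITT.

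Determining the therapeutic dose or doses is a primary objective. At the end of the study the evidence on the unselected doses lies largely in by-dose outputs: the four-group AUC1-7 summary in 8.1.1, the placebo differences for kidney function in 8.2.2.1, and the other four-arm efficacy tables. Those columns lose data.

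**Working it through.** **The plan's own figures.** SAP 4.1 gives power of 79% to 86% with strong effects at the medium and high doses, 66% to 67% when only the high dose is strong, and a one-sided type I error of 2.4%. The stated design was simulated as follows:
- four arms of 30, the dose with the largest t carried forward, a stop if all three one-sided p-values exceed 0.8, and 85 per arm in Part 2;
- inverse normal weights √(30/115) and √(85/115), and a closed test with unadjusted and Dunnett-adjusted Part 1 p-values;
- one-sided 0.025, SD 49, 100,000 runs per power scenario and 500,000 under the null.

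Power was 81.4%, 79.3% and 85.7% for a low-dose response of 60, 69.5 and 79, which matches the stated range. With only the high dose strong it was 69.2% (60/60/79), 67.4% (60/69.5/79) and 65.8% (69.5/69.5/79). The last two agree with the plan; the documents do not list the exact scenarios. Type I error was 2.51%, close to 2.4% given a simulation SE of about 0.07 points in 50,000 runs. None of these runs uses the excluded patients, so the confirmatory figures do not depend on how they are handled.

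**Inputs for the size of the exclusion.**
- Recruits during the interim analysis: "170 patients will enroll in Part 2 with an estimated 50 patients during the interim analysis" (protocol synopsis).
- Allocation: "using a 1:1:1:1 allocation ratio in Part 1" (Protocol 5.1). The synopsis and Section 3.1 apply the same ratio during the interim analysis. Two of the four arms are later dropped.
- Planned sizes: 30 per arm in Part 1 and 85 per arm in Part 2 (SAP 4.1), so pooled placebo is 30 + 85 = 115.
- SD of AUC1-7: 49 mL/min (SAP 4.1).

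**Patients dropped.** 50 × 2/4 = 25. If interim-period patients on placebo and the selected dose count towards the 170 in Part 2, total randomised is 290 + 25 = 315. The dropped share is then 25/315 = 7.9% of all randomised, and 25/(60 + 25) = 29% of those on unselected doses.

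**Precision for one unselected dose.** Its size is 30 with the exclusion and 30 + 25/2 = 42.5 without.
- SE of the arm mean = 49/√n: 49/√30 = 8.95 and 49/√42.5 = 7.52 mL/min, a 16% reduction.
- SE of dose minus pooled placebo = 49 × √(1/n + 1/115): 10.05 and 8.80 mL/min, a 12% reduction.
- 95% CI half-width for that difference: 1.96 × 10.05 = 19.7 and 1.96 × 8.80 = 17.2 mL/min.

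**Sensitivity to recruitment.** The 30 and 70 are an assumed range around the protocol's 50.

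| Interim-period recruits | Dropped | Share of randomised | Arm size if kept | SE of arm mean | SE of difference | Reduction in SE of difference |
|---|---|---|---|---|---|---|
| 30 | 15 | 4.9% | 37.5 | 8.00 | 9.21 | 8% |
| 50 | 25 | 7.9% | 42.5 | 7.52 | 8.80 | 12% |
| 70 | 35 | 10.8% | 47.5 | 7.11 | 8.45 | 16% |

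**The case against.** The strongest reply is that little of consequence moves. The monitoring committee picks the dose before these patients' results are in, the Emax model is an interim output, and inferential comparisons of the other efficacy endpoints involve only the selected dose and placebo. The patients stay in the safety summaries and in all listings. The handling also looks deliberate: the SAP change history says text was added on assigning interim-period recruits to analysis sets. All of this stands. It limits the effect mainly to descriptive columns and by-dose estimates for two dropped doses. It does not explain why a set called ITT departs from the protocol's definition with no entry in Section 12.

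It can also be said that 8.2.2 is only loosely worded, because ITT Combined is a defined term that carries its exclusion with it. That is a fair reading of 8.2.2 alone. Table 12-1 is harder to set aside, since it refers to the safety analysis, which takes everyone.

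A reader might infer more than the documents support, in four ways:
- That ITT Part 1 is itself wrong because it keeps these patients. It is not: keeping them carries out the protocol's instruction to place them in the Part 1 population.
- That the sensitivity-analysis exception corresponds to nothing in 8.1.4. The analysis of adjudicated Part 1 data there may be the one meant, although it is also described as a repeat of the interim analysis. The supportable criticism is that the exception is not named.
- That the SAP discards the dose-response information altogether. It does not: the definition of PP Day 1-7 Combined leaves these patients in, subject to its other criteria.
- That the confirmatory result is compromised. Part 1 enters the combination test as the interim p-value, and Part 2 uses only the selected dose and placebo.

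**Conclusion.** The point holds as a departure from the protocol and an inconsistency within the SAP that changes reported by-dose efficacy results. About 25 randomised patients would be missing from ITT Combined and the four-arm efficacy summaries, and each unselected arm would be summarised on 30 patients instead of about 42. Including them reduces the SE of that arm's mean AUC1-7 by 16% and the SE of its difference from pooled placebo by 12% (8% to 16% over the assumed range).

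These figures rest on the protocol's estimate of 50 recruits, equal allocation, the planning SD of 49 mL/min and planned arm sizes. They ignore site effects and any drift between parts. Actual recruitment will set the true count. Power and type I error of the primary test, the selected dose versus placebo comparison and the safety analyses do not change.

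**What to change.** Make ITT Combined all randomised patients, as in Protocol 7.5, and use it for every four-arm efficacy summary. That needs three deletions in the SAP:
1. the exclusion in 4.3.2;
2. the second bullet in Section 4 on interim-period recruits, while keeping its statement that their safety data are analysed;
3. the matching exclusion in the first sentence of Section 4 on secondary and other endpoints. If this one is missed, the SAP still contradicts itself.

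Then check that 4.3.3.1, 8.2.2 and Table 12-1 agree with the restored definition. Leave ITT Part 1, ITT Part 1 Interim, ITT Part 2 and the combination test as they are. If the sponsor wants the reduced set, report it in 8.1.4 as a named sensitivity analysis, not under the ITT label. Deleting the bullet also removes the only mention of the unnamed exception, so 8.1.4 should say what was intended.

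The cost is SAP wording and the corresponding table specifications. No new data are needed, because these patients are already part of the trial and its listings.
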